2.10 Design and theoretical / conceptual framework

This trial will be a multi-centre, pragmatic, individually randomised, open-label, parallel group trial with an integrated health economic evaluation. The design and theoretical framework will follow the IDEAL guidelines for conducting a clinical trial using an already CE-marked device, in line with the European Medical Device Regulation[23].

Methods for protecting against bias and contamination.

Selection bias: Treatment allocation will be concealed prior to randomisation using a bespoke randomisation system. To ensure clinicians have equipoise, we will assess the screening logs and examine reasons why patients have not been enrolled into the study.

Performance and detection bias (unblinded study): The nature of the trial intervention precludes masking of patients or care providers following randomisation. We will mitigate against potential bias in the absence of blinding, by using an objective measurable primary outcome (duration of mechanical ventilation (days)), and collecting data on intubation and readiness to extubate, and reasons why this might not occur as planned, to confirm consistency across randomised groups and assess performance bias on the part of treating clinicians. Intensive care clinical charts provide contemporaneous, hour by hour records of the patient's physiology and current treatments. Source verification (from clinical records) and hospital computer records will be used to minimise the risk of reporting bias. The main clinical and resource utilisation outcomes of this trial (e.g., ventilation status (hourly); death; level 2/3 care; adverse events, antibiotic uses) are recorded contemporaneously on patient clinical records and hospital information systems. This will enable outcomes to be verified by both site staff and the coordinating centre. It will also not be possible to directly blind the WCTU (Warwick Clinical Trials Unit) trial team to treatment allocation, as this information will be collected on the patient clinical record forms and will be necessary to monitor and manage protocol deviations and compliance/adherence. However, the team will have some blinding regards the randomised intervention, whilst collecting the follow-up outcome data. At the pilot stages, we will assess the patient baseline characteristics at site level, to identify any outliers which may have resulted due to our inability to blind the trial. The trial statistician, who has no role in decision-making with regards the conduct of the trial, will be unblinded and this will also facilitate linkage with the DMC.

Attrition bias: Most of the outcome data will be collected during the hospital stay. It is our experience that in this patient group (ICU patients) withdrawal rates are typically <3% (see sample size section below). On the rare occasions that a patient or their legal representative chooses to withdraw from the trial we will seek their permission to retain data collected up until that point and to continue to collect the main outcome data. Our experience is that patients are normally happy to proceed on this basis. These approaches should minimize the risk of attrition bias. For this reason, we anticipate very low levels of attrition and therefore no attrition bias (e.g., withdrawal rates for ICU studies include RECOVERY-RS 1%[24]; BREATHE 0% [25]; HARP-2 0.5%[26]; REST 1.7% [27]).

Reporting bias: We will register and publish our protocol prior to the end of recruitment. In addition, we will finalise our statistical analysis plan and the health economics plan before the trial finishes the recruitment of patients. All amendments to these finalised documents will be made available to ensure transparency.

Follow-up data (at 2 and 6 months) collected from patients will be limited to a single health-related quality of life and healthcare resource use questionnaires.

Treatment fidelity: To ensure the standardisation of the delivery of the intervention across the sites, a detailed training programme will be delivered (as detailed in section 2.6). Our progression criteria for moving from the pilot to main trial includes adherence and crossover criteria. We will closely monitor and assess treatment fidelity throughout the pilot study, obtain feedback from sites and enhance any processes to ensure that the delivery of both interventions is as protocolised. In the event of evidence of non-adherence, this will be flagged to the site research team. The site research team will then investigate events through discussion with the clinical team and, where appropriate, report this as a protocol deviation. Where necessary, further training will be provided.

Crossover and non-compliance: Cross-over will be defined as those patients who move from standard care to the advanced airways system post randomisation allocation. This will be discouraged. Non-compliance will be defined when patients move from the advanced airways system to standard of care, without reaching the endpoint (as stated in section 2.3). Both crossover and noncompliance will be monitored during the pilot study and the main trial. We will work very closely with sites, especially if a site has a higher rate of non-compliance/cross-over, to assist in over-coming any challenges, through education and further training and sites with persistent high non-compliance/cross-over rates will be closed. We will also assess the impact of these using statistical methods through the Estimand framework (as detailed in the statistical analysis plan in Section 6.2.2).

2.11 Blinding

Due to the nature of the trial interventions, it is not possible to blind hospital staff members or patients to treatment allocation.

2.12 Co-enrolment into other trials

This is detailed in section 4.5 CoReCCT Master Protocol.

2.13 End of trial

The trial will end when all participants have completed their 6-month follow-up, or receipt of routinely collected data, including resolution of data queries and data cleaning. The trial management group and research staff will review data entered and address any data queries prior to database lock.

The trial will be stopped prematurely if:

- Mandated by the Ethics Committee.
- Following recommendations from the Data Monitoring Committee (DMC).
- Funding for the trial ceases

The Research Ethics Committee will be notified in writing within 90 days when the trial has been concluded or within 15 days if terminated early.

3. METHODS AND ASSESSMENTS

3.1 Schedule of delivery of intervention and data collection

Table 1 summarises the trial schedule of events and timing of data collection.

Table 2 Trial assessments

	Timing of assessment				
	Baseline	Hospital stay	Hospital discharge	2 months	6 months
Eligibility assessment	✓				
Deferred consent ^a / Consent/ consultee ^b agreement	✓	✓*			
Baseline data collection	✓				
Randomisation	✓				
Intervention	✓	✓			
Critical care/ hospital stay data			✓		
Survival status		✓	✓	✓	✓
Quality of life (EQ-5D-5L) and health resource use questionnaire				✓	✓
Safety reporting		✓	✓		
^a not in Scotland ^b in Scotland referred to as welfare guardian/nearest relative *- only applicable if consultee agreement/deferred consent used as basis for initial enrolment					

3.2 Long term follow-up assessments

Long-term follow-up will be conducted at 2 months and 6 months following the *last* randomisation in the CoReCCT domain trials.

Follow-up questionnaires at 2 months and 6 months will capture health-related quality of life and healthcare resource use. The 6 month questionnaire will be sent out even if the 2 month questionnaire is not completed and returned. These questionnaires will usually be completed by the participant online and may be completed by postal questionnaire or over the phone. In the event that a participant is unable to complete the questionnaire (e.g.

neurological deficit), it may be completed on the participant's behalf by someone that has a good awareness of their health state (e.g. relative/ carer).

Long-term follow-up will be coordinated by WCTU. Prior to sending out follow-up questionnaires WCTU will wherever feasible liaise with the recruiting hospital to ensure that the participant has not died.

4. ADVERSE EVENT MANAGEMENT

In order to accurately assess and report SAEs relevant to PROTECT Airways, the CoReCCT Master Protocol must be read in conjunction with section 4.1 below.

Section 7 of the CoReCCT Master Protocol includes the CoReCCT Safety Reporting Flowchart and provides details on these adverse event management topics:

Definitions of SAEs

Assessing and reporting SAEs

Causality Assessment of SAEs

Expectedness Assessment of Related SAEs

Expedited Reporting of Related and Unexpected SAEs to REC

4.1 Pre-Specified Complications

As per the CoReCCT Safety Reporting Flowchart, adverse events that 1) occur at sites between randomisation and hospital discharge and 2) are not present on the CoReCCT Exemption List, must be reviewed for their presence on the PROTECT Airways Pre-Specified Complications List as given below (Table 2)

The duration of mechanical ventilation from randomisation to liberation is the primary objective of this study. Therefore, any clinically relevant intubation and mechanical ventilation related event occurring from the time of randomisation until ICU discharge will be recorded as pre-defined trial outcomes (see as listed in Safety Outcomes Section 2.2 above and SAE reporting exemptions below).

Table 3 Pre-Specified Complications List (safety outcomes)

Pre-Specified Complications List (safety outcomes)

Adverse event rates related to endotracheal tube intubation within one hour of intubation or tube change if allocated to intervention arm:

- *Traumatic insertion, bleeding*
- *Injury to the throat or trachea*
- *Dental damage*
- *Failed intubation*
- *Aspiration during intubation*
- *Pneumothorax*
- *Obstruction or kinking of the endotracheal tube*
- *Cuff leak*

- *Unintentional extubation*

Adverse event rates related to endotracheal tube intubation after one hour of intubation, or tube change if allocated to intervention arm, up to ICU discharge

- *Tracheal stenosis*
- *Vocal cord injury / paralysis / arytenoid dislocation*
- *Hoarse voice / voice changes*
- *Sinusitis*
- *Laryngo-tracheal stenosis*
- *Tracheomalacia*
- *Obstructive fibrinous tracheal pseudo membrane*
- *Pressure injuries related to tube securing or pressure from tracheal tube.*
- *Tracheo-oesophageal fistula*

- *C-spine and spinal cord injuries due to intubation*

As per the CoReCCT Safety Reporting Flowchart, if the event is present on the Pre-Specified Complications List, the event must be recorded on the appropriate CRF as an outcome and does not need to be reported as an SAE. If the event is not on the list, it must be assessed for seriousness and the remainder of the flowchart should be followed to determine next steps.

The target population for the trial is the broad group of patients that require intubation and mechanical ventilation. These patients are the sickest in the hospital and are at risk of physiological deterioration, including the need for increased organ support, and death. These events are captured as clinical outcomes.

All-cause mortality at ICU discharge, hospital discharge 2 and 6 months post randomisation will be captured as an outcome.

4.2 Expectedness Assessment

SAEs which are considered possibly related, probably related, or definitely related to the trial intervention will be assessed for expectedness by the Sponsor. This expectedness assessment may be supported by items such as, but not limited to; associated domain working instructions and published literature.

5. DATA MANAGEMENT

Further details on data management are provided in sections 6 and 10 of the CoReCCT Master Protocol.

5.1 Data collection and management

Full details are listed in section 10 of the CoReCCT Master Protocol.

22(32)

5.2 Data Shared with Third Parties

Full details are listed in section 12 of the CoReCCT Master Protocol.

5.3 Archiving

Full details are listed in section 13 of the CoReCCT Master Protocol.

5.4 Data access and quality assurance

Full details are listed in section 10 of the CoReCCT Master Protocol.

6. STATISTICAL ANALYSIS

6.1 Power and sample size

We will recruit 2194 patients (1097 per arm) in total (using 90% power, 5% alpha level). Using methods based on survival analysis, the following parameters have been used for the estimation of the sample size:

- *Duration of invasive mechanical ventilation (control arm)*. Based on 133,291 admissions to 209 adult, general critical care units 1 April 2011 – 31 March 2012, the median duration of mechanical ventilation, for this trial was taken as 6 days [29].
- *Minimal clinically important difference*: In the ongoing NIHR HTA MARCH trial [30] and the BREATHE study [25], a clinically important difference of 1 day was considered to be meaningful (as defined by clinical ICU-based investigators and patient and public representatives).
- *Loss-to-follow-up*: Using the ICNARC Quarterly Quality Report Manchester Royal Infirmary, Intensive Care/High Dependency Unit (1 April 2018 to 31 March 2019) based on 2,535 patients the mortality of ventilated patients averaged at 25.6% (ICNARC, Case Mix Programme Report, 2019- obtained from ICNARC). Thus, the sample size has been inflated, to account for this loss to follow-up.
- *Withdrawal rate*: We anticipate a low rate of withdrawal of patients, as the primary outcome will be measured during the hospital stay. In our previous trials, we have consistency observed low rates of withdrawals (e.g. RECOVERY-RS 1% [24] ; BREATHE 0% [25]; HARP-2 0.5% [26]; REST 1.7% [27]). For this trial we have very conservatively assumed a withdrawal rate of 3%.
- From the above, we derive a hazard ratio of 1.2 (i.e., 6/5 days). It is anticipated that the hazards may not be constant over time (as assumed for the exponential distribution) and that the hazards are quite likely to decrease over time (as observed in the BREATHE study [31]). For this reason, the Weibull distribution may be more of an appropriate distribution, as it computes a shape parameter, p , which allows for non-constant hazards. Using the data from the BREATHE study [31], we derived the shape parameter, p , as 0.901. The hazard ratio is adjusted for this parameter and the sample size computed using the survival analysis methods.

We will review the sample size parameters with the DMC at the end of the pilot stage, using the observed data.

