2.3 Aims and objectives

Objectives:

- (1) Conduct an internal pilot study to confirm the feasibility of a large-scale multicentre trial.
- (2) To conduct a UK-wide multi-centre, open-label, pragmatic, individually randomised, parallel group trial and economic evaluation to determine the clinical and cost effectiveness of an advanced airways protection device versus conventional endotracheal tubes (with and without basic subglottic manual suction and standard cuff) in patients with respiratory failure requiring mechanical ventilation. The outcomes are duration of mechanical ventilation, survival, ICU, and hospital stay outcomes and health-related quality of life.
- (3) Estimate, in an integrated economic evaluation, the cost-effectiveness of an advanced airways protection device versus the conventional endotracheal tubes.

Justification of outcomes

We have worked with patients, the public, researchers and clinicians to determine both our primary and secondary outcomes. This clinical effectiveness trial comprises key core outcomes from the Core Outcomes in Ventilation Trials (COVent) core outcome set and NICE guidelines for ventilation trials and NICE guidelines [5, 12, 13].

Primary effectiveness outcome

The primary variable (outcome) of interest is the duration of mechanical ventilation as measured from time from randomisation to first successful unassisted breathing, measured in days. This outcome is one of the 'COVenT' core outcomes for trials of interventions intended to modify the duration of mechanical ventilation[14]. To clarify:

- Unassisted breathing is defined as no inspiratory support or extracorporeal lung support
- Success is defined as maintaining unassisted breathing at 48 hours.
- Duration includes time receiving extracorporeal lung support, invasive mechanical ventilation and non-invasive ventilation delivering volume or pressure support ventilation.
- Duration excludes time receiving high-flow oxygen therapy and continuous positive airway pressure.
- Patients with a tracheostomy in situ may still achieve successful unassisted breathing.

Secondary outcomes - refer to CoReCCT master protocol for core clinical outcome set.

Effectiveness

- *Duration of endotracheal intubation*: time from randomisation to endotracheal extubation (in hours).
- Ventilator Associated Pneumonia (VAP): Diagnosed by treating clinician with commencement of antibiotics [16] from randomisation up to ICU discharge.

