6.2.2 Statistical analysis plan

Primary outcome analyses

The outcome summaries and analyses will adopt the Estimand framework (as cited by the ICH E9 (R1) addendum on Estimand and sensitivity analyses in clinical trials) [33].

Summary measure and the primary Estimand: The duration of mechanical ventilation (in days) will be summarised using median, interquartile range, mean and standard deviation. The statistical analysis for this outcome will be done using the treatment policy strategy (i.e. intention to treat). Time-to event (survival models) analysis will be used to estimate the treatment effect by summarising hazards odds ratios (and 95% confidence intervals), using both unadjusted and adjusted (for site and adjusting for e.g. age and illness severity (APACHE II)) estimates. Kaplan-Meier plots will be used to display the duration of ventilation accommodating for the censored values. Intercurrent events (ICEs) and strategies for handling ICEs: post-randomisation events that may affect the interpretation of the primary outcome will include: (a) death (ICE 1); (b) cross-over (ICE 2); (b) non-compliance (including discontinuation of treatment) (ICE 3). The ICE 1 will be analysed using a composite strategy and applying competing risk models. Fine and Gray competing risk regression will be used to assess duration of ventilation, in the presence of death[34]. Competing risk regression models address the situation when more than one mutually exclusive endpoint is possible: in this case, successful extubation or death. This analysis provides a sub-distribution hazard ratio (SHR), the magnitude of which is affected by both the time to coming off the ventilator and the probability of death. SHR assesses the association between an intervention and extubation, accounting for the existence of the alternative outcome of death. The ICE 2 and ICE 3 will be analysed using the principal stratum strategy. For the ICE 2, we will

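### The protocol does not say whether the design hazard ratio of 1.18 is cause-specific or sub-distribution, nor which model carries the primary test; if it is Fine and Gray, 90% power for a one-day gain needs assumptions the protocol does not state

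*Protocol*

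**What the plan says.** **Sample size (Protocol 6.1).** "We will recruit 2194 patients (1097 per arm) in total (using 90% power, 5% alpha level"). The inputs are a control median of 6 days, a target for which "a clinically important difference of 1 day was considered to be meaningful", a hazard ratio of 1.2 from 6/5, a Weibull shape of 0.901 used to adjust it, 3% withdrawal, and 25.6% mortality of ventilated patients. The mortality is entered as loss to follow-up: "Thus, the sample size has been inflated, to account for this loss to follow-up". No sub-distribution hazard ratio (SHR), death timing or effect on mortality is given.

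**Analysis (Protocol 6.2.2).** The section first plans unadjusted and adjusted time-to-event estimates under a treatment policy strategy. It then makes death an intercurrent event: "Fine and Gray competing risk regression will be used to assess duration of ventilation, in the presence of death". It notes that the SHR depends on the probability of death as well as on time to coming off the ventilator. For display, "Kaplan-Meier plots will be used to display the duration of ventilation accommodating for the censored values".

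**Event.** Section 6.2.2 names the two competing endpoints as "in this case, successful extubation or death". Section 2.3 defines the primary outcome as "time from randomisation to first successful unassisted breathing, measured in days". There, success must be maintained at 48 hours, non-invasive ventilation with pressure or volume support counts as ventilation, and success is possible with a tracheostomy in place.

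**The concern.** A hazard ratio taken from a ratio of medians, with deaths removed as losses, describes the liberation rate among patients still alive and ventilated. Fine and Gray keeps patients who died in the risk set, so its ratio answers a different question. If the device speeds liberation and leaves the death hazard alone, the SHR is closer to 1 than the cause-specific ratio. The 90% may then not belong to the model that supplies the primary result.

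The same uncertainty reaches the futility rule in section 6.4, which computes conditional power from a hazard ratio of 1.2 without naming a scale. The event matters too: a model of extubation and a model of unassisted breathing would not count the same patients at the same times.

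**Working it through.** **1. Reproduce the stated size** (inputs from 6.1; two-sided 5%, since one-sided does not reproduce).
- Adjusted hazard ratio: 1.2^0.901 = 1.1785.
- Freedman events: (1.96 + 1.2816)² × (2.1785/0.1785)² = 1,565, or 783 per arm.
- Inflation: 783 / (1 − 0.256 − 0.03) = 783 / 0.714 = 1,097 per arm, 2,194 in total. This is exact.
- Power check (Schoenfeld) at 2,194 × 0.714 ≈ 1,566 events: Φ(ln 1.1785 × √1566 / 2 − 1.96) = 0.90.

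Dividing events by the share of patients expected to have the event is also the usual competing-risk inflation. The step is therefore valid on either scale, provided 1.18 is on the scale of the test.

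**2. Why the scales differ.** Assume 25.6% of controls die before liberation, a death hazard proportional to the liberation hazard, and the same death hazard in both arms.
- Control patients eventually liberated: 0.744.
- Treated: 1.1785 × 0.744 / (1.1785 × 0.744 + 0.256) = 0.774, so 22.6% die before liberation.
- Ratio of cumulative sub-distribution hazards at the plateau: ln(0.226) / ln(0.256) = 1.09.

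The ratio starts near 1.18 and drifts to 1.09. Fine and Gray reports an average, about 1.126 in simulation.

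**3. Fine and Gray power at 2,194.** Simulation with 2,000–3,000 trials per row, 3% withdrawal, control median 6 days, cause-specific hazard ratio 1.1785 and equal death hazards, unless the row says otherwise. Every death assumption is mine, because the protocol gives none.

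| Assumption | SHR | Power |
|---|---|---|
| 25.6% die first, proportional death hazard | 1.126 | 66% |
| 25.6%, constant death hazard | 1.13 | about 70% |
| 25.6%, follow-up cut at 28 days | 1.14 | 72–74% |
| 25.6%, exponential times with hazard ratio 1.2 | 1.143 | 76% |
| 25.6%, deaths early (Weibull shape 0.6) | 1.11 | 57% |
| 25.6%, deaths late (shape 1.5 to 2) | 1.15–1.16 | 80–85% |
| 10–15% die first | 1.13–1.14 | about 72–80% |
| 25.6%, device also cuts death hazard by 10% | 1.17 | about 88% |
| 1.1785 is itself the SHR | 1.18 | about 91% |

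In the rows at 25.6% with an unchanged death hazard, a cause-specific test with deaths censored has about 91% power (96% in the exponential row, where the ratio is 1.2).

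**4. One-day shift on the cumulative-incidence scale.** Take a control curve 0.744 × (1 − exp(−q(t/6)^0.901)) that reaches 50% at day 6, so q = −ln(1 − 0.5/0.744) = 1.115. At day 5 it is 0.455. The SHR that moves the 50% point to day 5 is ln(0.5) / ln(1 − 0.455) = 1.142. With 2,194 × 0.744 × 0.97 = 1,583 events, power is 75%.

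**5. Display, if deaths were censored.** Under the model of step 2, Kaplan-Meier would show 94% liberated at day 28 against a cumulative incidence of 73%, and a median of 6.0 against 7.3 days.

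**The case against.** Several points on the other side stand.

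- **The arithmetic is right.** A reader might infer that the inflation for mortality is an error. It is not.
- **Fine and Gray is not clearly the powered test.** If the ordinary hazard ratio is primary with deaths censored, 90% is correct. A flat statement that the trial has 66–75% power, or would miss a one-day benefit one time in three, is not supported.
- **The 25.6% is mortality of ventilated patients.** The protocol does not say these deaths all precede liberation. If some follow it, the shortfall is smaller. Nor does it say whether the 6-day median treats deaths as censored.
- **Kaplan-Meier censoring of deaths is an inference.** Section 6.2.2 mentions censored values without saying which; withdrawals are censored too. The contrast in step 5 is conditional on this.
- **There is a safeguard.** Section 6.1 commits to reviewing the sample size parameters with the data monitoring committee after the pilot.

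The last point is only a partial answer. Pilot data can show how many patients die before liberation and when, but cannot say which scale 1.18 was meant on. Reading 1.18 as the SHR rescues the 90%, but with 25.6% deaths among controls it implies 0.256^1.1785 = 20.1% in the device arm, a mortality benefit that section 6.1 does not state.

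**Conclusion.** The concern holds as a mismatch left open between sections 6.1 and 6.2.2, not as a proven loss of power. The stated 90% is right for a cause-specific hazard ratio of 1.18 with deaths censored, or for an SHR of 1.18. It is not right for Fine and Gray if the device gives a one-day gain and leaves the death hazard unchanged. Power there is about 66–76% under the simpler models with 25.6% dying first, and 57% to 85% once death timing is varied.

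An unchanged death hazard is not the same as unchanged mortality, because faster liberation leaves less time at risk. In an extreme model, where exactly the same share dies in each arm and only survivors are liberated faster, power is about 20–22%. The spread is the reason to state the assumptions and not a single corrected figure.

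The event named in 6.2.2 does differ from the one in 2.3. That is a separate wording fault with no bearing on these power figures.

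**What to change.** 1. In 6.2.2, name the one model that carries the primary test.
2. In 6.1, state whether 1.18 is a cause-specific hazard ratio or an SHR. If Fine and Gray is primary, restate power for a one-day gain with explicit assumptions on mortality before liberation, death timing and effect by arm, and show the range. Alternatively, make the cause-specific hazard ratio primary, for which 90% stands, and report Fine and Gray and mortality beside it.
3. State the same scale for the hazard ratio in the futility rule of 6.4.
4. If deaths would be censored in the Kaplan-Meier plots, show cumulative-incidence curves for liberation and for death, and read medians from those.
5. In 6.2.2, replace the extubation event with successful unassisted breathing as defined in 2.3.

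The cost is wording in three sections and a less favourable stated power if Fine and Gray is kept as primary. No extra patients are required to make the statement correct.
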